^a For all Grade ≥ 3 hematological or non-hematological AEs that are NOT Selinexor or Temozolomide related, after consultation with the Medical Monitor and at the discretion of the Investigator, selinexor may be maintained

^b For all Selinexor-related AEs, if the below prescribed dose reductions/interruptions result in a stabilization of ≥ 4 weeks, a re-escalation may be considered after approval from the Medical Monitor.

All dose modifications should be based on the worst preceding toxicity.

Note: It is strongly encouraged that the Investigator dose reduces or interrupts one drug at a time for those AEs that are thought to have multifactorial causes.

3.3.2.1.1 Infection

Patients with active uncontrolled or suspected infections should have treatment withheld until the infection has clinically resolved and/or the patient is clinically stable. When ready to resume dosing, treatment may continue at the original dose. Patients may continue antibiotic therapy for prolonged periods while re-initiating their treatment at the discretion of the Investigator.

3.3.2.1.2 Renal Insufficiency

Baseline renal insufficiency does not appear to affect tolerability of Selinexor and renal dysfunction should not preclude continued dosing with Selinexor, even for patients on dialysis. If a patient is undergoing dialysis, Selinexor should be given after dialysis procedure because the effect of dialysis on Selinexor plasma levels has not yet been studied. Selinexor can lead to increased creatinine and the majority of these cases are associated with hypovolemic conditions (e.g., represent “pre-renal” azotemia). Dose modifications or interruptions and appropriate hydration typically reverse the increased creatinine.

3.3.2.1.3 Conditions not requiring Selinexor dose reduction

The following conditions are exceptions to the dose-modification guidelines. Selinexor does not need to be held for alopecia of any grade, or for electrolytes or serum analyte (e.g., urate) abnormalities that are reversible with standard interventions.

3.3.2.2 Temozolomide (TMZ)

3.3.2.2.1 During concomitant radiotherapy

A complete blood count should be obtained weekly. Adjustments to the dose of Temozolomide and Selinexor will be made at the direction of the PI or study chairperson.

| Toxicity and Intensity | Supportive Care and Dose Adjustment Guidelines |
|-------------------------------|--|
| Platelets | |
| >75k | Continue both drugs. |
| Grade 2, >50-75k | Hold TMZ Hold Selinexor Continue RT. Recheck CBC, when platelets >75k restart TMZ and selinexor |

| | |
|-----------------|---|
| Grade 3, 25-50k | Hold TMZ. Discontinue Selinexor. Continue RT. Recheck CBC, when platelets >75k restart TMZ |
| Grade 4, <25k | Hold TMZ Discontinue Selinexor Hold RT Recheck CBC, when platelets >50k restart RT When platelets >75 k restart TMZ |
| ANC | |
| >1.5 | Continue both drugs |
| Grade 2, >1-1.5 | Hold TMZ Hold Selinexor Continue RT Recheck CBC when ANC 1.5 restart TMZ and selinexor |
| Grade 3, 0.5-1 | Hold TMZ Discontinue Selinexor Continue RT Recheck CBC, when ANC >1.5 restart TMZ |
| Grade 4, <0.5 | Hold TMZ Discontinue Selinexor Continue RT Recheck CBC, when ANC >1,5 restart TMZ, |

3.3.2.2.2 Following the completion of chemoradiation

Beginning 1-month post-RT, the adjuvant temozolomide will be given per standard of care.

3.4 QUESTIONNAIRES (FOR ENGLISH SPEAKING PATIENTS ONLY)

MD Anderson Symptom Inventory for Brain Tumors (MDASI-BT) ([Appendix D](#)) will be performed at baseline, at completion of radiation and at all subsequent follow-up visits.

PROMIS Depression, PROMIS Anxiety, and NeuroQoL assessments ([Appendix E](#) and [Appendix F](#)) will be performed at baseline, at completion of radiation and at all subsequent follow-up visits.

PRO-CTCAE ([Appendix G](#)): Patients will complete a baseline PRO-CTCAE before starting treatment, at completion of radiation and at all subsequent follow-up visits if the patient is able. It takes 5-10 minutes to complete each questionnaire. It will only be completed by the patient, unless changes in vision or weakness make this difficult. If this occurs, then the caregiver may read the questions to the patient or assist with marking the answers as described by the patient. A patient caregiver may complete the questionnaires as a patient-preference proxy if the patient's deficits preclude self-report.

All questionnaires are allowed to be completed within +/- 7 days from the scheduled dates.

Every attempt will be made to collect this data from every patient at each time point. If the patient is a non-English speaker the data will not be collected.

3.5 STUDY CALENDAR

| Procedure | Screening | Baseline ¹ | Radiation ² (every day up to 6 weeks) | Follow-up (Total 3 yrs) ^{8, 10} | | |
|--|-----------|-----------------------|---|--|--------------------------------|---------------------------------|
| | | | | 1 month | Every 2 months for 2 yrs | Every 3 months for 3rd yr |
| History & PE | X | X | | X | X | X |
| Karnofsky Performance | X | X | | X | X | X |
| Neurological function & Mental Status | X | X | | X | X | X |
| Vital signs incl Weight | X | X | X | X | X | X |
| Height | X | | | | | |
| Pathology review incl molecular CNS panel | X | | | | | |
| Treatment | | | | | | |
| On treatment visit (OTV) evaluation once per week | | | X | | | |
| Temozolomide (Daily) ³ | | | X | | | |
| Selinexor ⁴ | | | X | | | |
| Toxicity assessment ^{5, 9} | | | X | X | X | X |
| Labs (Please refer section 2.2.2 for details) | | | | | | |
| Hematology ^{6a} | X | X | X | X | X | X |
| Chemistries ^{6b} | X | X | X | X | X | X |
| Thyroid function tests | | X | | | | |
| Pregnancy Test (urine/serum) | X | X | | | | |
| Hepatitis A, B and C testing | X | | | | | |
| HIV testing | X | | | | | |
| Radiographic (Please refer section 2.4 for details) | | | | | | |
| MRI | X | X | | X | X | X |
| CT scans | | X | | | | |
| Questionnaires (Please refer section 3.4 for details) | | | | | | |
| QoL questionnaires per MDASI-BT (Appendix D) ⁷ | | X | X | X | X | X |
| PROMIS Depression, PROMIS Anxiety, and NeuroQoL (Appendix E) ⁷ | | X | X | X | X | X |
| PRO-CTCAE (Appendix F) ⁷ | | X | X | X | X | X |

¹ Tests done at screening do not need to be repeated on baseline (C1D1) if performed within 7 days prior to enrollment except physical exam, KPS, vital signs, neurological exam, performance and mental status, and urine pregnancy test. Screening laboratory evaluations do not need to be repeated if done within 14 days prior to enrollment.

- ² Patients will be treated with 2Gy daily RT plus 75mg/m² temozolomide for six weeks with Selinexor given once or twice a week depending on dose level.
- ³ Regarding temozolomide dosing details, please refer to section [**3.2.2**](#).
- ⁴ Administered per section [**3.1.5**](#).
- ⁵ Assessment of acute toxicity (CTCAE Version 5.0 and RTOG Acute Morbidity score. (see [**Appendix B**](#) and [**Appendix C**](#))
- ⁶ Laboratory evaluation weekly during radiation.
 - a. Complete blood count with differential and platelets, PT/INR, PTT
 - b. Serum chemistries: LDH, AST, ALT, alkaline phosphatases, bilirubin (total and direct), BUN, serum creatinine, serum electrolytes, glucose, calcium, magnesium, phosphorous, uric acid, albumin, amylase, lipase
- ⁷ QOL assessment will be performed at baseline, at completion of radiation and at all subsequent follow-up visits. The questionnaires are allowed to be completed within +/- 7 days from the scheduled dates.
- ⁸ May be completed by remote visit with a member of the study team (e.g., if the patient is not able to return to the NIH CC). A patient may be referred to their local provider or asked to come to the NIH CC for an in-person assessment, if clinically indicated, and at the discretion of the PI. In the case of any visits with participants' local providers, records will be obtained. Follow-up evaluations should occur at one month after the completion of therapy, followed by at least every 2-month intervals for the first 2 year(s), and then at least every 6 months thereafter for a total of 3 years following completion of radiation/ Temozolomide/ Selinexor.
- ⁹ Toxicity assessment, vital signs and weight measurement may be done weekly during the on treatment visit and as needed.
- ¹⁰ All follow-up appointments will take place within +/- 7 days of the designated timepoint.

3.6 RADIATION THERAPY GUIDELINES

3.6.1 Scheduling

Radiation therapy will be administered daily Monday-Friday at NCI ROB unless the treatment schedule requires amendment in the event of inclement weather or federal holidays. All the protocol related follow-up appointments will occur at NCI ROB at the NIH Clinical Center.

3.6.2 Technique

Radiation therapy dose will be administered on consecutive treatment days, 5 fractions per week via a linear accelerator using 6 MV photons or greater. Interruptions for holidays will be permitted, and any missed days will be added on to the end of treatment. CT simulation will be performed in the treatment position with the patient immobilized using a thermoplastic mask.

Both EORTC and RTOG treatment volumes are permitted as described below:

| EORTC treatment volumes (single phase) | RTOG treatment volumes (two phases) |
|--|--|
| Single Phase (Treated to 60 Gy in 30 fractions) | Phase I (Treated to 46 Gy in 23 fractions) |
| GTV: Surgical resection cavity plus any residual enhancing tumor (postcontrast T1 weighted MRI scans). CTV: GTV plus a margin of 2 cm PTV: CTV plus a margin of 3-5 mm | GTV1: Surgical resection cavity plus any residual enhancing tumor (postcontrast T1 weighted MRI scans) plus surrounding edema (hyperintensity on T2 or FLAIR MRI scans). CTV1: GTV1 plus a margin of 2 cm (if no surrounding edema is present, the CTV is the contrast enhancing tumor plus 2.5 cm). PTV1: CTV plus a margin of 3-5 mm |
| | Phase II (Treated to 14 Gy in 7 fractions) GTV2: Surgical resection cavity plus any residual enhancing tumor (postcontrast T1 weighted MRI scans) CTV2: GTV2 plus a margin of 2 cm PTV2: CTV2 plus a margin of 3-5 mm |

3.6.3 Target coverage and dose limits

The volume of PTV covered by the prescription dose must represent $\geq 95\%$ of the PTV. A variation of $\geq 90\%$ coverage of the PTV will be accepted. As per ICRU criteria, the max point dose shall not exceed 107% of the prescribed dose.

3.6.4 Critical structures

The organs at risk in the field to be contoured include brain, brainstem, optic nerves, and optic chiasm. Normal tissue dose limits will be employed as per table below:

| OAR | Objective |
|--------------|--|
| Brainstem | D _{max} ≤60 Gy 1-10 cc > 59 Gy (Periphery) |
| Chiasm | D _{max} <55 Gy |
| Cochlea | Ideally one side mean <45 Gy |
| Eyes | Macula<45 Gy |
| Optic Nerves | D _{max} <55 Gy |

3.7 COST AND COMPENSATION

3.7.1 Costs

NIH does not bill health insurance companies or participants for any research or related clinical care that participants receive at the NIH Clinical Center. If some tests and procedures are performed outside the NIH Clinical Center, participants may have to pay for these costs if they are not covered by an insurance company. Medicines that are not part of the study treatment will not be provided or paid for by the NIH Clinical Center.

3.7.2 Compensation

There will not be any compensation as part of the study.

3.7.3 Reimbursement

The NCI will cover the costs of some expenses associated with protocol participation. Some of these costs may be paid directly by the NIH and some may be reimbursed to the participant/guardian as appropriate. The amount and form of these payments are determined by the NCI Travel and Lodging Reimbursement Policy.

3.8 CRITERIA FOR REMOVAL FROM PROTOCOL THERAPY AND OFF STUDY CRITERIA

Prior to removal from study, effort must be made to have all subjects complete a safety visit approximately 30 days following the last dose of study therapy.

3.8.1 Criteria for removal from protocol therapy

- Completion of 6 weeks of RT
- Progressive disease as defined in **6.3.1**
- Participant requests to be withdrawn from active therapy
- Unacceptable Toxicity as defined in section **3.3**
- Investigator discretion
- Positive pregnancy test

3.8.2 Off-Study Criteria

- Completed study follow-up period
- Participant requests to be withdrawn from study
- Death
- Investigator discretion
- Non-compliance with follow-up visits or protocol mandated procedures
- Participant lost to follow up
- Investigator decision to end the study

3.8.3 Lost to Follow-up

A participant will be considered lost to follow-up if he or she fails to return for three scheduled visits and is unable to be contacted by the study site staff.

The following actions must be taken if a participant fails to return to the clinic for a required study visit:

- The site will attempt to contact the participant and reschedule the missed visit within two weeks and counsel the participant on the importance of maintaining the assigned visit schedule and ascertain if the participant wishes to and/or should continue in the study.
- Before a participant is deemed lost to follow-up, the investigator or designee will make every effort to regain contact with the participant (where possible, 3 telephone calls and, if necessary, an IRB approved certified letter to the participant's last known mailing address or local equivalent methods). These contact attempts should be documented in the participant's medical record or study file.
- Should the participant continue to be unreachable, he or she will be considered to have withdrawn from the study with a primary reason of lost to follow-up.

4 CONCOMITANT MEDICATIONS/MEASURES

- Prophylactic concomitant treatments with a 5-HT3 antagonist and olanzapine 5 mg for men and 2.5 mg for women must be provided 3 days prior to and during treatment with each dose of selinexor. Olanzapine may be administered as needed on days 6 and 7 during week of selinexor treatment.
- PJP prophylaxis should be given during the concurrent chemoradiation phase of treatment. Acceptable forms of treatment include oral trimethoprim-sulfamethoxazole and aerosol pentamidine as is left to the discretion of the treating physician.
- Other cancer chemotherapy, immunotherapy, or investigational agents may NOT be administered to patients in the active course of treatment on this study.
- Patients will receive corticosteroids as needed for symptoms of cerebral edema as clinically indicated. Attempts to wean patients from steroids should be made as indicated by improvement or stabilization of neurologic symptoms. Any initiation of steroids or increase in dose thereof will be documented.
- All patients with a seizure history will be maintained on their existing anticonvulsant medication.

- Radiation therapy side effects include fatigue, nausea and vomiting and possible worsening of preexisting neurological symptoms. These will be managed using general best supportive care and corticosteroids may be initiated at the discretion of the treating radiation oncologists and taper as needed depending on clinical status once irradiation has been completed.
- The ROB staff physician, nurse practitioner and research nurse will frame the support infrastructure required to assist with the patient's care in the event of serious treatment toxicity. The pain and palliative team, will be consulted as needed to address end of life issues and disposition as has been standard procedure for all ROB patients to date.

5 CORRELATIVE STUDIES FOR RESEARCH

None.

6 DATA COLLECTION AND EVALUATION

6.1 DATA COLLECTION

The PI will be responsible for overseeing entry of data into a 21 CFR Part 11-compliant data capture system provided by the NCI CCRand ensuring data accuracy, consistency and timeliness. An enrollment log will be maintained in the regulatory binder/file which is the only location of personal identifiers with unique subject identification number. Imaging will be digitally archived and processed using computer software in the Radiology department of the Clinical Center, NIH, and the Radiation Oncology Branch, NCI. The principal investigator, associate investigators/research nurses and/or a contracted data manager will assist with the data management efforts. Primary and final analyzed data will have identifiers so that research data can be attributed to an individual human subject participant.

All adverse events, including clinically significant abnormal findings on laboratory evaluations, regardless of severity, will be followed until return to baseline or stabilization of event. Document AEs from the first study intervention, Study Day 1, through 30 days after the subject received the last study drug administration.

An abnormal laboratory value will be recorded in the database as an **AE only** if the laboratory abnormality is characterized by any of the following:

- Results in discontinuation from the study
- Is associated with clinical signs or symptoms
- Requires treatment or any other therapeutic intervention
- Is associated with death or another serious adverse event, including hospitalization
- Is judged by the Principal Investigator to be of significant clinical impact
- If any abnormal laboratory result is considered clinically significant, the investigator will provide details about the action taken with respect to the test drug and about the patient's outcome.

End of study procedures: Data will be stored according to HHS, FDA regulations, and NIH Intramural Records Retention Schedule as applicable.

Loss or destruction of data: Should we become aware that a major breach in our plan to protect subject confidentiality and trial data has occurred, this will be reported expeditiously per requirements in section [7.2.1](#).

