8.2 ASSESSMENT OF SAFETY EVENTS

AE information collected will include event description, date of onset, assessment of severity and relationship to study product and alternate etiology (if not related to study product), date of resolution of the event, seriousness and outcome. The assessment of severity and relationship to the study product will be done only by those with the training and authority to make a diagnosis and listed on the Form FDA 1572 as the site principal investigator or sub-investigator. AEs occurring during the collection and reporting period will be documented appropriately regardless of relationship. AEs will be followed through resolution.

SAEs will be:

- Assessed for severity and relationship to study product and alternate etiology (if not related to study product) by a licensed study physician listed on the Form FDA 1572 as the site principal investigator or sub-investigator.
- Recorded on the appropriate SAE report form, the medical record and captured in the clinical database.
- Followed through resolution by a licensed study physician listed on the Form FDA 1572 as the site principal investigator or sub-investigator.

For timeframe of recording adverse events, please refer to section **6.1**. All serious adverse events recorded from the time of first investigational product administration must be reported to the sponsor with the exception of any listed in section **8.4**.

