8.4 WAIVER OF EXPEDITED REPORTING TO CCR

Progression of the malignancy disease (including fatal outcomes) should NOT be reported as an SAE during the study or within the safety reporting period. Any sudden or unexplained death should be reported as an SAE. If there is any uncertainty about a finding being due solely to progression of malignancy disease, the finding should be reported as an AE or SAE, as appropriate.

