10.4.4 Safety Analyses

Adverse events will be coded as per the CTCAE v5.0. Each AE will be coded once for each patient based on the maximum severity during the assessment period. The relationship of AEs to study intervention will be recorded in addition to the onset date, end date, severity, expectedness, and outcome.

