14.3.2 Toxicity to brain

This list represents the effects of radiation that have been noted for patients to this area of the body. Each person may have different reactions. It is not possible, therefore, to predict any individual's exact side effects.

Reactions can occur during shortly after, or long after the treatment courses and may include, but are not necessarily limited to the following:

| DURING OR SHORTLY AFTER TREATMENT COURSE | AFTER TREATMENT COURSE (MONTHS TO YEARS) |
|---|--|
| COMMON Skin redness and irritation in area treated Hair loss in area treated, including eyebrows Tiredness Worsening of neurologic symptoms present prior to radiation | COMMON Scalp discoloration and thickening Mild decrease in memory or ability to think Permanent thinning or loss of hair in treated area including eyebrows |
| UNCOMMON Tiredness, headache, weakness, numbness, or other neurologic deficit which may require steroid treatment Nausea, vomiting, weight loss Increase in seizure activity if already present Dry eyes | UNCOMMON Permanent loss (death) of brain cells Development of seizures Severe memory loss Cataracts in eyes Hearing loss Dry eyes |
| RARE Decreased blood cell count Excessive need of sleep | RARE Death of brain cells causing swelling in the brain and requiring long term steroid treatment, hospitalization, or/or surgery Loss or decrease of vision Change in hormone levels from the pituitary |
| OTHER | EXTREMELY RARE Development of new tumors in scalp, skull or brain Difficulty with control of water balance, thirst, loss of salts from body Loss of function specific to the area affected such as: vision, sensation, memory, judgement, motor skills Damage to retina causing blindness Damage to blood vessels leading to stroke or may be fatal. |

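### Adverse event recording ends 30 days after an undefined last study drug, so three years of scheduled late-toxicity scoring reach no planned safety summary

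*Combined protocol and SAP*

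**What the plan says.** Section 6.1 sets the recording rule: "Document AEs from the first study intervention, Study Day 1, through 30 days after the subject received the last study drug administration". Events that begin inside that window are followed to baseline or stabilisation (6.1) and through resolution (8.2).

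Section 8.2 relies on that rule: "For timeframe of recording adverse events, please refer to section" 6.1. Its sentence on serious events gives a start and no end: "All serious adverse events recorded from the time of first investigational product administration must be reported to the sponsor". Section 8.4 says that progression "should NOT be reported as an SAE during the study or within the safety reporting period", but that period is defined nowhere.

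The study calendar (3.5) marks toxicity assessment at 1 month, two-monthly over the first two years, and three-monthly in the third. Footnote 5 describes the content as "Assessment of acute toxicity (CTCAE Version 5.0 and RTOG Acute Morbidity score", yet it points to both Appendix B (acute) and Appendix C (late). Section 6.4 adopts both appendices for radiation-related toxicity. Footnote 8 words the third-year interval differently: "and then at least every 6 months thereafter for a total of 3 years".

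Among brain-radiation effects arising months to years after treatment, 14.3.2 includes "Death of brain cells causing swelling in the brain and requiring long term steroid treatment, hospitalization, or/or surgery".

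Section 10.4.4 plans a summary of CTCAE events: "Each AE will be coded once for each patient based on the maximum severity during the assessment period". It does not define that period and does not mention the RTOG late score.

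**The concern.** Section 1.2.10 says selinexor is used here as a radiation sensitizer. It is added to 60 Gy to the brain, and 1.2.8 reports no prior clinical experience of that combination. Safety and tolerability are part of the primary objective (1.1.1). Late injury to normal brain is one of the hazards a reader would want described before a dose goes into phase 2.

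The plan schedules the visits and supplies the scale, then closes adverse event recording almost at the start of follow-up and names no analysis of the late scores. A new event at month 5, for example brain necrosis needing surgery, could be seen and scored in clinic and still appear in no planned safety table. Section 10.4.7 also rules out tabulating individual participant data, so no listing would show it.

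Because study drug is not defined, the end of the window can also move relative to the DLT window that determines the primary endpoint.

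**Working it through.** **The plan's own figures.** The documents give no late-toxicity figure. The computed figures in 10.2 are the escalation probabilities and the sample size. With P(escalate) = (1−p)³ + 3p(1−p)²(1−p)³, true DLT rates of 10% to 60% give .906, .709, .494, .309, .172 and .082. These match the stated .91, .71, .49, .31, .17 and .08. The numbers of patients also reproduce: 6+6+9 = 21, 3+3+9 = 15, 21+3 = 24. None of these depends on late events.

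**Visits after the window, if study drug means concurrent selinexor and temozolomide.** Temozolomide stops when radiation ends (3.2.2), so recording ends 30 days after radiation and only the 1-month visit can fall inside.
- Calendar column: 1 + 24/2 + 12/3 = 17 visits; 16/17 = 94% fall after the window.
- Footnote 8 minimum: 1 + 24/2 + 12/6 = 15 visits; 14/15 = 93%.
- If the two-monthly visits are counted from month 1 instead, one visit drops out of each total: 15 of 16, or 13 of 14.

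In time, 30/(3 × 365.25) = 2.7% of the follow-up period is covered. These counts assume a patient followed for all three years. As an illustration allowing for deaths, take exponential survival with the 16.1-month median in 1.2.1, counted from the start of radiation (an assumption). About 95% of expected post-radiation observation time then still falls after the window, roughly 16.4 months per patient.

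**If study drug means selinexor only.** Take day 1 as the Monday of week 1, with 30 uninterrupted fractions at five per week (3.6.2). Radiation ends on day 40 and the DLT window (3.1.4, 10.1.1) on day 70. Last doses follow 3.1.5 and 3.2.1; level −1 is assumed to use the same weekday as level 1.

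| Level | Last selinexor | Recording ends (+30) | Days before DLT window ends |
|---|---|---|---|
| −1 | day 23 | day 53 | 17 |
| 1 | day 30 | day 60 | 10 |
| 2 | day 32 | day 62 | 8 |
| 3 | day 39 | day 69 | 1 |

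The 1-month visit, at ±7 days, spans days 63 to 77. At levels −1, 1 and 2, recording closes before that visit can take place.

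**If on-study adjuvant temozolomide counts.** Section 3.1.2 allows it on study or through the patient's own oncologist, so the window would run longer for some patients only.

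**Which meaning applies.** The title page lists both drugs under one IND. Section 14.1.1 uses the term for selinexor, and the diaries cited in 3.2.2.1 for oral study drugs cover selinexor alone. The documents do not settle it.

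**What a late summary could show.** No late-event rate is given. For assumed rates of 5%, 10% and 20%, the chance of at least one event, 1−(1−p)ⁿ, is 37%, 61% and 87% with 9 patients, and 66%, 89% and 99% with 21, ignoring deaths before onset. With 0 of 9 events, the one-sided 95% upper bound is 1 − 0.05^(1/9) = 28%.

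**The case against.** Two stronger readings are tempting, and the documents support neither.

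A reader might infer that SAE reporting stops at 30 days. Section 8.2 refers to 6.1 only for the timeframe of recording adverse events. Its SAE sentence has no end date, 8.3 requires submission within 24 hours of awareness without a cut-off, and 8.7 puts no 30-day limit on the sponsor's duty for serious unexpected reactions. The 30-day stop is one inference; what can be said is that the end date is unclear.

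A reader might also infer that late harm lies wholly outside the recorded data. It does not. Appendix C is a scoring form with a physician signature line. MRI, neurological function and mental status are marked at every follow-up visit, and section 4 has steroid starts and increases documented. MDASI-BT, Neuro-QoL and PRO-CTCAE continue through follow-up, and 10.4.8 summarises QOL scores by visit. Those summaries, however, are neither graded toxicity nor specified by dose level.

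Other parts of the opposing case stand:
- Most of the serious late effects in 14.3.2 are labelled uncommon, rare or extremely rare.
- Preclinical work (1.2.4) found no radiosensitisation of normal fibroblast lines and no loss of protein synthesis in astrocytes.
- The MTD rests on acute DLTs, and late toxicity is not a named endpoint.
- With at most 9 patients at the MTD and no comparator, a late summary can only be descriptive.
- Footnote 8 states a minimum that three-monthly visits satisfy, so the third-year difference is a matter of wording.

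None of this supplies a recording period, analysis or reporting rule for new late events.

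**Conclusion.** The concern holds as a gap between what is scheduled and what is recorded as an adverse event and summarised. New-onset late toxicity falls outside the adverse event dataset, 10.4.4 covers only CTCAE events over an undefined period, and no analysis uses the Appendix C score. The safety part of the primary objective would be answered without a late component.

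The size depends on the undefined term. If the concurrent drugs define it, about 93% to 94% of scheduled follow-up visits come after the window in a patient followed for three years. If selinexor alone defines it, recording ends 1 to 17 days before the DLT window under uninterrupted radiation. That does not show that DLTs would be missed, because 3.1.4 and 10.1.1 set their own window; it shows two periods that must be made to agree. If adjuvant temozolomide counts, the window differs between patients. The survival share and late-event rates above are illustrative. This should be corrected, but it does not undermine the dose-finding design.

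**What to change.** - **6.1:** Define study drug. Set the end of adverse event recording no earlier than 30 days after the later of radiation completion and the last concurrent drug. Keep that limit for unrelated events. Through the existing three-year follow-up, also record RTOG late events of grade 3 or higher, and CNS or eye events that are related and either grade 3 or higher or serious.
- **8.2:** State the SAE end date, and state that related late SAEs are reported. Define or remove the reporting period named in 8.4.
- **10.4.4:** Define the assessment period. Tabulate worst RTOG late grade by dose level, descriptively and apart from the DLT-window table, with the number of patients still under follow-up.
- **3.5:** Reword footnote 5 so that it covers late scoring under Appendix C, and align the third-year interval between the calendar column and footnote 8.

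The cost is protocol wording, one follow-up form page, late grading at some visits that footnote 8 allows to be remote or with a local provider, and some additional late SAE reports. The visits and scales are already scheduled. The MTD rule, escalation table and sample size stay as they are.
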